#### **11.4 Analysis of Exploratory Endpoints:**

1. Clinical outcomes such as tumor response rate, progression-free survival, and overall survival for cohort 3 (recurrent BRAF-V600 mutated high-grade primary brain tumors not included in the cohort 1 and cohort 2). The standard definitions of these outcomes will be used as described above. The outcomes will be summarized and presented descriptively.
2. Encorafenib and binimetinib concentrations in enhancing brain tissue and cerebrospinal fluid (surgical cohort): descriptive summary on mean and standard deviation of drug will be reported. Additional analyses are summarized in Section [9.6.1](#).
3. Putative mechanisms of drug resistance are defined as identified genomic or functional alterations in post-treatment tissue that are not present, or are present in a much smaller variant allele frequency (VAF), in pre-treatment tissue, and that could contribute to decreased drug sensitivity. Candidate mutations will be measured using the methods described in Section [9.6.2](#). These results will be manually curated and confirmed against known gene lists.
4. Functional inhibition of the ERK signaling pathway: the functional inhibition of the ERK signaling pathway is defined by the measurements of phospho-ERK and RSK protein, quantitated relative to total ERK. Due to the exploratory nature, the pathway changes after drug exposure will be reported using descriptive summary.

5. BRAF-V600 DNA mutant fraction: the mutant fraction is measured as the number of BRAF V600E or –K transcripts relative to BRAF wild-type transcripts, corrected for differences in sequencing efficiency and the quantity of starting material. The mutant fraction in CSF and plasma will be collected over multiple time points during the study. The fraction change overtime will be presented as a liner or non-linear trend after data checking. Descriptive summary at each individual time point and multiple time points will be presented graphically.

A more detailed description of exploratory correlatives are provided in Section [9.6](#).

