### Clinical Pharmacokinetics (PK) and Drug-drug Interactions of Encorafenib

The pharmacokinetics (PK) of encorafenib were studied in healthy subjects and patients with solid tumors, including advanced and unresectable or metastatic cutaneous melanoma harboring a *BRAF* V600E or K mutation. After repeat once-daily dosing, steady-state conditions were reached within 15 days, exposure being approximately 50% lower compared to Day 1, with a median half-life ~4 hours, and moderate intersubject variability (percent coefficient of variation [%CV]) of area under the curve (AUC; 12.3% to 68.9% over a range of doses). The PK of encorafenib has been shown to be approximately dose proportional after multiple doses, with any deviation from dose proportionality likely due to auto-induction of CYP3A4.

The human ADME study in healthy subjects showed that encorafenib is at least 86% absorbed and has a preferential distribution to plasma as compared to blood. Encorafenib was mainly eliminated via metabolism, with low levels of unchanged encorafenib detected in urine and feces. The dose was equally recovered in urine and feces (47.2% in each matrix) and the renal clearance was estimated to be 1.8%.

Results from a food-effect clinical study in healthy subjects have indicated that the influence of food on the PK of encorafenib is mild and not clinically relevant; therefore, encorafenib can be taken without regard to food. In combination studies, when administered with binimetinib, PK parameters of encorafenib were similar to those observed in the single-agent study.

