## 9.2 Table of Additional Required Observations - Surgical Arm

Patients on the surgical arm will be required to undergo all baseline observations as detailed for the medical arm in Section [9.1](#) prior to surgical resection with the exception of research CSF collection. Upon resumption of encorafenib and binimetinib after surgery (as detailed in Section [4.1](#)), the Cycle 1-12 observations and off-treatment observations as detailed in the medical arm will also be observed. Observations listed below are additional on day of surgery.

Patients on the Medical Arm undergoing a clinically-indicated surgery for their brain tumor while on study should also adhere to specimen collection guidelines for Surgical Arm patients (below).

**Table 9.2** Required Observations on Day of Surgery – surgical arm patients

	Means of Collection	2 hours prior to surgery	Just prior to surgery (after induction of anesthesia)	Prior to tumor disturbance	During surgical resection	After closure
Encorafenib		1, 2				
Binimetinib		1, 2				
Blood	PD/Resistance/Circulating Tumor DNA: 10mL x 1		2,3			
	cTDNA:EDTA Lavender top 10mL x 2		2,3			
	PK: EDTA Lavender top 10mL x 1		2,3			2,3
Cerebrospinal Fluid	sterile container, 6mL			2,3		
Tumor Tissue	0.05-0.10 cm  contrast enhancing tumor				2,4	
	0.05-0.10 cm  non-enhancing tumor				2,4	
	0.5 cm  contrast enhancing tumor tissue				2,4	
	20 unstained slides					5
Documentation	On CRFs	2	2	2	2	2

- 1 – Encorafenib and Binimetinib should both be administered orally with a small quantity of water as necessary 2 hours before the patient’s surgical time.
- 2 – Exact time for all drug administration and sample removal should be charted on case report forms (CRFs).
- 3 – The blood and CSF samples should be collected as close in time to the resection as possible. In the event that a specific blood tube is not available, a reasonable substitution (in volume only) may be made; however, the blood collected should not exceed that as outlined in the consent document. The same tube-type should be collected in all instances (e.g., two 6mL lavender top / EDTA tubes may be substituted for a 10mL tube).
- 4 – Three surgical specimens should be removed and flash-frozen. See Section [9.6.5](#).
- 5 - 20 unstained FFPE slides should be requested after tissue specimen is processed and final pathology report is complete. See Section [9.6.5](#). This is in addition to archival tumor tissue obtained for all study patients.

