## 9.6 Correlative Studies

### 9.6.1 Pharmacokinetic Assessment (All Surgical Patients): Exploratory

This correlative study is mandatory for all patients in the surgical arm. It is also optional for patients on the medical arm who progress while on treatment and undergo a clinically indicated resection while on study drugs.

Blood, cerebrospinal fluid, and tissue samples will be collected on the day of surgery at time points specified in Section [9.2](#). Details for the collection, processing, storage, and shipment of samples are provided in the **Laboratory Manual**.

We hypothesize tumor drug concentration will directly correlate with functional ERK inhibition, and may correlate with extent and duration of response in individual patients. Levels of total (protein-bound and unbound) encorafenib and binimetinib, as well as the active metabolite of each parent compound, will be measured as continuous variables using validated LC/MS methods in order to calculate the tumor-to-plasma ratio as an estimate of tumor permeability. (51) We will compare drug concentrations between enhancing and non-enhancing brain, and CSF. This assay will be performed by the ABTC-associated Applied Pharmacology Core at Johns Hopkins led by [name].

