### 9.6.5 Overview of Biospecimen Collection on Surgical Arm

Patients with a history of BRAF-V600E/K mutated glioma who are planning to undergo surgical tumor resection and are eligible to participate in this study (based on inclusion/exclusion criteria in Sections [3.2](#) and [3.3](#)) may participate in the surgical arm. Patients on the medical arm who experience likely progression and require a clinically indicated surgery are also eligible if they continue drug until the day of surgery. All patients in this cohort should take their last dose of binimetinib and encorafenib two hours prior to surgery. At the time of this clinically indicated surgery, biospecimens will be collected, after the induction of general anesthesia, in the following order:

- 1) Prior to tumor manipulation: Whole blood (total of 40 mL) and cerebrospinal fluid (6 mL).
  - a. Blood will typically be obtained from an arterial line and/or venous line placed as part of standard of care, placed immediately on wet ice, and processed as described in the **Laboratory Manual**.

- b. CSF will be obtained in one of three ways per discretion of the neurosurgeon ± principal investigator, placed immediately on wet ice, and processed as described in the **Laboratory Manual**. Determination as to the method of CSF extraction (specifically, whether or not a lumbar puncture is indicated) will be determined prior to surgery and patient will confirm on consent form.
    - i. By Ommaya reservoir access prior to the surgical procedure.
    - ii. By lumbar puncture after the induction of anesthesia so as to induce no additional discomfort to the patient.
    - iii. During surgery, from cisternal aspiration, if the cistern were to be opened as part of the planned surgical procedure.
    - iv. During surgery, from ventricular aspiration, if the ventricle were to be encountered as part of the planned surgical procedure.
- 2) At tumor manipulation: Enhancing and non-enhancing brain tumor tissue.
- a. After frozen section confirmation of glioma and confirmation with the pathologist that sufficient material has been obtained for clinical diagnostic processing (grading, sub classification, and the relevant genetic testing), additional tumor specimens will be obtained for this study and processed as described in the **Laboratory Manual**.

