  - b. The specimen locations will be determined by the neurosurgeon based on MRI and tissue appearance with one intended to be in enhancing and the other in non-enhancing brain per MRI-contrast pre-operative image. The sample location will be noted with MRI wand and correlated with pre-operative MRI scan.
- 3) At closure: Whole blood (10 mL), obtained as above.
- 4) After tissue is processed: 20 unstained FFPE slides from current resection.

20 unstained slides from the repeat resection should be requested and processed as outlined in the **Laboratory Manual** and shipped, along with a copy of the associated pathology report.

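### Tissue and CSF drug concentrations in about 6 patients are summarised by mean and SD, and the tumour-to-plasma ratio has no stated summary and no rule for which of two plasma draws is its denominator

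*Combined protocol and SAP*

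**What the plan says.** **Summary statistic.** Section 11.4 item 2 covers "Encorafenib and binimetinib concentrations in enhancing brain tissue and cerebrospinal fluid (surgical cohort"), for which a "descriptive summary on mean and standard deviation of drug will be reported". It then adds that "Additional analyses are summarized in Section" 9.6.1. The word arithmetic is not used, but it is the natural reading.

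**Ratio.** Section 9.6.1 measures total drug and active metabolite "in order to calculate the tumor-to-plasma ratio as an estimate of tumor permeability". It names neither a summary statistic for the ratio nor the plasma sample that forms its denominator.

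**Plasma draws.** The row of Table 9.2 labelled "PK: EDTA Lavender top 10mL x 1" is marked at two times: just before surgery, once anaesthesia is induced, and after closure. Section 9.6.5 gives the same order. The first blood is taken before the tumour is touched, tissue follows, and then: "At closure: Whole blood (10 mL), obtained as above".

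**Timing.** The footnotes to Table 9.2 ask for blood and CSF to be taken near the time of resection, and for the times of doses and of specimen removal to be charted on the CRF. No analysis text says how those times are used.

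**Context.** Section 11.2 plans 6 surgical patients and states that nothing in the trial is decided on their outcome. Under Section 9.6.1, medical-arm patients who are resected while on drug may also contribute, hence about 6.

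**The concern.** There are two separate weaknesses.

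1. **Mean and SD at this sample size.** Concentrations cannot be negative and tend to be right-skewed. In six patients one high value can pull up the mean and inflate the SD, so that a reader who forms the usual interval gets impossible concentrations. The typical level is then overstated and the spread is hard to interpret.

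2. **An open denominator.** Tissue is removed between two plasma draws. If plasma changes over the operation, the ratio depends on which draw is used, and a fixed choice of draw ties it partly to the length of the operation. With no rule written down, the choice can be made after the data are seen.

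At stake is how well the trial describes drug levels in tumour and CSF, which is exploratory objective 2, and whether the ratio can be compared between patients and with other studies. The primary response endpoint is untouched.

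**Working it through.** **Inputs from the documents**
- Encorafenib half-life: "with a median half-life ~4 hours" (Section 2.2).
- Encorafenib between-subject CV for plasma AUC: 12.3% to 68.9% over a range of doses (Section 2.2).
- Binimetinib: variability described in words only, and no half-life (Section 2.3).
- Last dose of both drugs: two hours before surgery (Section 4.1).
- Cohort size: 6 (Section 11.2).

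**Assumptions not in the documents**
- Concentrations are log-normal.
- The plasma AUC CV stands in for the unknown tissue and CSF CV.
- The two PK draws are 2 to 6 h apart.
- Both draws fall in the elimination phase.

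**Step 1: the plan's own figure.** Section 11.2 gives 90% power at a true 80% probability of blood-brain barrier penetration, and a 0.93 chance of rejecting a true 30%. No decision rule is stated. The figures reproduce with a rule of at least 4 of 6:
- Power = P(X ≥ 4 | n = 6, p = 0.8) = 0.2458 + 0.3932 + 0.2621 = 0.901.
- P(X ≤ 3 | n = 6, p = 0.3) = 0.930.

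The sample-size statement is therefore sound under that inferred rule. It treats each patient as penetrating or not, and the text gives no threshold for that. It does not settle how concentrations or ratios are summarised.

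**Step 2: arithmetic against geometric mean.** For log-normal data the expected ratio is √(1 + CV²).
- CV 12.3%: √(1 + 0.0151) = 1.008, about 1% higher.
- CV 68.9%: √(1 + 0.4747) = 1.214, about 21% higher.

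**Step 3: mean and SD in samples of 6.** This used 200,000 simulated log-normal samples of 6, with log-scale SD = √ln(1 + CV²), which is 0.623 at CV 68.9%.
- CV 68.9%: mean minus 2 SD is below zero in 61% of samples. The sample mean exceeds the sample geometric mean by 15% at the median, with 5th and 95th percentiles of 4% and 41%.
- CV 12.3%: mean minus 2 SD was below zero in none of the samples, and the two means nearly coincide.

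**Step 4: first or second draw as denominator (encorafenib).** With mono-exponential decline and a 4 h half-life, the ratio on the closure draw divided by the ratio on the induction draw is 2^(t/4), where t is the gap in hours.

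| Gap between draws (assumed) | Closure vs induction denominator, 2^(t/4) | Either draw vs plasma at the midpoint, 2^(t/8) |
|---|---|---|
| 2 h | 1.41 | 1.19 |
| 4 h | 2.00 | 1.41 |
| 6 h | 2.83 | 1.68 |

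The last column is the error against time-matched plasma if tissue is removed halfway between the draws.

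**Step 5: what cannot be computed.** With dosing two hours before surgery and no time-to-peak in the documents, the first draw may be near peak or still in absorption. The fall between draws could then be smaller than in the table, or plasma could even rise. For binimetinib there is no half-life to put in the formula.

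**The case against.** The strongest reply has four parts.

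- **Mean and SD are legitimate descriptive statistics.** The wording does not forbid medians, ranges or listings, and with six patients anything can be recomputed later. This is true, but the plan commits to the one summary that serves skewed small samples worst, and at the upper documented CV it would often imply negative concentrations.
- **The sampling plan does address timing.** A reader might infer from the two draws that there is no time alignment at all. The documents do not support that: Table 9.2 asks for sampling near the resection and for charted times. What is missing is the analysis rule that uses those times.
- **The quoted sentence concerns concentrations.** A reader might take mean and SD to be the stated summary for the ratio as well. It is not; no summary is stated for the ratio.
- **The size is uncertain.** A reader might settle on two-fold as an upper limit for the denominator effect. It is not a limit. It is the value at exactly one half-life between draws, applies to encorafenib only, and assumes that both draws are in decline. Against time-matched plasma the error is smaller for at least one draw. The CVs in Step 2 are for plasma AUC, so carrying them to tissue and CSF is an assumption.

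It is also fair that log-linear interpolation rests on plasma actually declining, so it needs a fallback. These points limit the size of the concern and shape the remedy. They do not supply the missing denominator or make mean and SD a good summary here.

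**Conclusion.** The point stands as a low-priority improvement in two parts.

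**Concentrations.** Mean and SD is a poor choice for about 6 positive, skewed values. If tissue and CSF variability resembles the encorafenib plasma AUC range, the mean overstates the geometric mean by about 1% to 21%. At the top of that range, mean minus 2 SD is negative in about 61% of samples of 6. At the bottom of the range the choice hardly matters.

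**Ratio.** The plan calculates it without a summary statistic or a denominator rule, although two timed plasma draws bracket tissue removal. For encorafenib the choice of draw shifts the ratio 1.41-fold at an assumed 2 h gap and 2.83-fold at 6 h, under a 4 h half-life with both draws in decline. Direction and size are not assured if the first draw is near peak. Nothing numerical can be said for binimetinib.

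A reader might go on to infer that a trial conclusion is at risk, or that the ratio is the cohort's main result. The documents support neither. Exploratory objective 2 concerns concentrations, and Section 11.2 rests no decision on this cohort.

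**What to change.** **Section 11.4 item 2.** List individual values with median and range, and report geometric mean and geometric CV in place of mean and SD alone. State how values below the quantification limit are handled, since a geometric mean cannot take zeros and neither Section 11.4 nor Section 9.6.1 gives a rule.

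**Section 9.6.1.** Define each patient's ratio against plasma matched to the charted tissue-removal time:
- When plasma is declining between the draws, interpolate log-linearly: C = C₁^(1−w) × C₂^w, where w is the fraction of the interval between draws that has elapsed at tissue removal.
- Otherwise use the draw nearest in time.
- Show the ratio against each single draw as sensitivity, and summarise ratios in the same way as concentrations.

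**Cost.** Analysis wording and a little more analysis work. Both plasma samples and all times are already collected, so no procedure, visit or sample size changes. The price is reliance on an interpolation assumption, which the single-draw sensitivity results make visible.

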## **12.0 STUDY ADMINISTRATION**

The Investigator must maintain adequate and accurate records to enable the conduct of the study to be fully documented and the study data to be subsequently verified.

### **12.1 Investigator’s Study File**

The Investigator’s Study File must contain all essential documents as required by ICH E6, including IRB and governmental approvals with correspondence, informed consent forms, patient enrollment and identification logs, drug accountability records, staff *curriculum vitae*, authorization forms and other appropriate documents/correspondence etc.

### **12.2 Source Data/Documents**

Patient source documents used to record key efficacy/safety parameters, independent of the CRFs, may include for example, patient hospital/clinic records, original laboratory reports, ECG read-outs, MRI reports, pathology and special assessment reports, etc.

Source documents are part of the study documents and must be maintained, and direct access to source documents made available upon request, for monitoring visits, IRB review, audits or inspections. All source documents used to verify answers on CRFs will be uploaded to RAVE, including all documentation to prove eligibility criteria was meet.

### **12.3 Document Retention and Archiving**

The Investigator must keep all study documents on file for at least 5 years after completion or discontinuation of the study. Subsequently, the Sponsor will inform the Investigator when the study documents can be destroyed, subject to local regulations.

These files must be made available for inspection, upon reasonable request, to authorized representatives of Sponsor or regulatory authorities.

Should the Investigator wish to assign the study records to another party, or move them to another location, the Sponsor must be notified in advance.

If the Investigator cannot guarantee the archiving requirement at the investigational site for any or all of the documents, arrangements must be made between the Investigator and the Sponsor for appropriate storage.

## 12.4 Data Collection/Reporting

**Data collection for this study will be done exclusively through CTEP's Medidata Rave.**

Access to the trial in Rave is granted through the iMedidata application to all persons with the appropriate roles in the Regulatory Support System (RSS). To access iMedidata/Rave the site user must have an active CTEP IAM account (<https://eapps-ctep.nci.nih.gov/iam>). In addition, site users that are a member of the ABTC must have the Rave CRA role in RSS at the enrolling site.

Upon initial site registration approval for the study in RSS, all persons with Rave roles assigned on the appropriate roster will be sent a study invitation e-mail from iMedidata. Please note, site users will not be able to access the study in Rave until all required Medidata and study specific trainings are completed. Trainings will be listed in the upper right pane of the iMedidata screen.

Users that have not previously activated their iMedidata/Rave accounts will also receive an invitation from iMedidata to activate their account. If you have any questions, please contact the CTSU Help Desk at [name] or [[contact]](mailto:[contact]).

- All data are due within 14 days of evaluation time point. Please see Section [9.1](#) for evaluation time points. Note: Source documentation to verify each CRF must be uploaded into Rave.
- Serious Adverse Events, PHONE IMMEDIATELY, SEE SECTION [9.3](#)

This study will be monitored by the Clinical Data Update System (CDUS) Version 3.0. Cumulative protocol- and patient-specific CDUS data will be submitted electronically to CTEP on a quarterly basis by FTP burst of data. Reports are due January 31, April 30, July 31, and October 31. The ABTC Central Office is responsible for compiling and submitting CDUS data to CTEP for all participants and for providing the data to the Principal Investigator for review.

## 12.5 Study Monitoring

The ABTC Study Monitor (Sponsor) will remotely monitor the Investigator and study team on a regular basis throughout the study to verify the adherence to Good Clinical Practice (GCP), the protocol and the completeness, consistency and accuracy of the data being entered into the CRFs. The Study Monitor will also ensure that the study drug is being stored, dispensed, and accounted for according to specifications.

The Study Monitor will only conduct target on-site monitoring (See ABTC Monitoring plan for details). If on-site monitoring is necessary, the Investigator shall ensure that the study monitor has direct access to all required study data (source documents) during the visits. This includes all patient records needed to verify the entries in the CRFs, regulatory documents, pharmacy records or any other documents of concern.

The Investigator agrees to cooperate with the Study Monitor and ABTC to ensure that any deviations or issues detected in the course of monitoring visits are resolved.

